8 CONVENTIONS

8.1 Safety Data Conventions

Except as noted in Section 7.6, safety data will be handled according to the BMS safety data conventions⁴. This document includes descriptions on how to analyze AE data as well as how to handle partial dates, missing dates, and unknown end dates when analyzing safety data. If onset time of AEs is missing or incomplete, the onset date of AEs will be used to determine if the AEs will be included in the AE summary tables as follows.

- Non-serious AEs will be included in summary tables if the onset date/time is on or after the start of the study drug infusion until 24 hours after end of infusion in each treatment period of dosing.
- Serious AEs will be included in summary tables if the onset date/time is on or after the start date of study drug infusion until 30 days after the end of infusion of the last period.

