2 SCHEDULE OF ACTIVITIES

Table 2-1: Time & Event Schedule CV013020, Screening Period

Procedure	Screening Visit	Notes
Eligibility Assessments		
Informed Consent	x	A participant is considered enrolled only when a protocol specific informed consent is signed.
Inclusion/Exclusion Criteria	x	
Medical History	x	
Concomitant medications	x	
Echocardiography eligibility assessment	x	As described in the echocardiographic core lab manual, evaluation of image quality and assessment of ejection fraction
Safety Assessments		
Physical Examination	x	If the screening physical examination is performed within 3 days prior to first dosing then a single exam may count as both the screening and pre-dose evaluation. Includes height and weight.
Vital Signs	x	Includes body temperature, respiratory rate, and seated blood pressure and heart rate. Blood pressure and heart rate should be measured after the participant has been resting quietly for at least 5 minutes.
Adverse Events Assessment	x	SAEs must be collected from the date of the participant's Informed consent.
Local Laboratory Tests	x	Hematology, Serum chemistry, NT-proBNP or BNP (details in the protocol section 9.4.4)
Pregnancy Test (WOCBP only)	x	

Table 2-2: Time & Event Schedule CV013020, Treatment and Follow-up Study Periods

Procedure	Treatment Period					Notes
	Period 1 Day 1	Washout 5-28 Days	Period 2 Day 1	Washout 5-28 Days	Period 3 Day 1	
Safety Assessments						Washout between periods should be at least 5 days and no more than 4 weeks.
Weight	x		x		x	Weight pre-and end of the infusion in each treatment period.
Targeted physical examination	x		x		x	Based on subject's report since the screening visit. Includes temperature, signs and symptoms of congestion.
Vital Signs (Blood pressure and heart rate)	x		x		x	Prior to infusion. 30 minutes at first hour, then every 1 hour until discontinuation of infusion, then at 1 hour, 2 hour and 3.5 hour after end of infusion in each treatment period.
Peripheral Oxygen Saturation	x		x		x	Prior and end of the infusion in each treatment period, measured with a pulse oximeter device.
12 lead ECG	x		x		x	Prior to the infusion and after end of infusion in each treatment period.
Urinary output	x		x		x	From start of infusion to 3 hours after end of infusion in each treatment period.
Telemetry	x		x		x	From start of infusion to 3 hours after end of infusion in each treatment period.

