Adverse Events Assessment				x		Non-serious AEs will be collected from the start of the study drug infusion, until 24 hours after end of infusion in each treatment period of dosing in each period
					x	Serious adverse events must be collected from the date of Informed consent and will be assessed up to 30 days after the end of infusion of the last period.

Table 2-2: Time & Event Schedule CV013020, Treatment and Follow-up Study Periods

Procedure	Treatment Period					Notes
	Period 1 Day 1	Washout 5-28 Days	Period 2 Day 1	Washout 5-28 Days	Period 3 Day 1	
Concomitant Medications	x		x		x	Chronic heart failure medications to be taken during the treatment day (D1 of each period) will be withheld until the end of the study drug infusion in each treatment period.
Follow-up call	x		x		x	Follow-up call to be done at Day 2 of each period (will inquire about general status and occurrence of any AEs) and 30 days after the end of the infusion of the last period (will assess occurrence of any SAEs).
Local Laboratory Tests	x		x		x	Hematology and Serum chemistry (details in the protocol section 9.4.4). Can be performed within 24 hours of treatment day.
Central Laboratory Tests	x		x		x	Hematology, Serum chemistry, Biomarkers (details in the protocol section 9.4.4)
Pharmacokinetic (PK) sampling	x		x		x	PK sampling will be done pre-dose, 0.5 hour, 1 hour, 4.5 hours and 7 hours after the start of the infusion in each treatment period. In addition, PK samples should be taken when the dose is lowered or in case of early discontinuation (see protocol section 9.5)
Pregnancy Test (WOCBP only)	x		x		x	Can be performed within 24 hours of treatment day.
Efficacy Assessments						
Echocardiography	x		x		x	Prior to and before the end of the study infusion (between hour 4 and hour 5) in each treatment period. If study drug is interrupted prematurely, the echocardiography assessment should be done as soon

Table 2-2: Time & Event Schedule CV013020, Treatment and Follow-up Study Periods

Procedure	Treatment Period					Notes
	Period 1 Day 1	Washout 5-28 Days	Period 2 Day 1	Washout 5-28 Days	Period 3 Day 1	
						Washout between periods should be at least 5 days and no more than 4 weeks.
						as possible after study drug interruption. If the study drug is resumed after interruption, echocardiography should be repeated between hour 4 and hour 5 of the effective study drug infusion.

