9.2 Adverse Events

The definitions of an AE or serious adverse event (SAE) can be found in [Appendix 3](#).

AEs will be reported by the participant (or, when appropriate, by a caregiver, surrogate, or the participant's legally authorized representative).

The investigator and any designees are responsible for detecting, documenting, and reporting events that meet the definition of an AE or SAE and remain responsible for following up AEs that are serious, considered related to the study treatment or the study, or that caused the participant to discontinue before completing the study.

Contacts for SAE reporting specified in [Appendix 3](#)

9.2.1 *Time Period and Frequency for Collecting AE and SAE Information*

The collection of non-serious AE information begins at initiation of study treatment until 24 hours after discontinuation of the infusion at the time-points specified in [Section 2](#) the Schedule of Activities (Section 2). Non-serious AE information should also be collected from the start of a placebo lead-in period or other observational period intended to establish a baseline status for the participants.

Sections 5.6.1 and 5.6.2 in the Investigator Brochure (IB)³³ represent the Reference Safety Information to determine expectedness of serious adverse events for expedited reporting. Following the participant's written consent to participate in the study, all SAEs, whether related or not related to study drug, must be collected, including those thought to be associated with protocol-specified procedures.

All SAEs must be collected that occur during the screening period and within 30 days of discontinuation of dosing.

The investigator must report any SAE that occurs after these time periods and that is believed to be related to study drug or protocol-specified procedure.

- Medical occurrences that begin before the start of study treatment but after obtaining informed consent will be recorded on the appropriate section of the eCRF section.
- All SAEs will be recorded and reported to Sponsor or designee within 24 hours, as indicated in [Appendix 3](#).
- The investigator will submit any updated SAE data to the sponsor within 24 hours of this being available.

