6 STUDY PERIODS, TREATMENT REGIMENS AND POPULATIONS FOR ANALYSES

6.1 Study Periods

Screening for inclusion in the study will be performed up to 4 weeks before the first treatment day. After screening, study participants will be enrolled in the study according to their eligibility as per the inclusion and exclusion criteria, and will be randomized to 1 of the 6 sequences that will be conducted in parallel.

Each sequence has 3 periods. Study participants will be admitted to the study facility on the treatment day, which will be the Day 1 of each of the three periods. Study participants will remain in the study facility for approximately 3.5 hours post-dose and discharged on the same day, unless the investigator and the study team consider that an overnight stay is warranted. The treatment day of period 1 and period 2 are followed by a washout period of at least 7 days but no more than 4 weeks.

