7.6.1 Deaths

All reported deaths after a subject is enrolled (i.e., has signed the informed consent) will be listed separately by subject.

7.6.2 *Serious Adverse Events*

All reported serious adverse events (SAEs) will be listed by System Organ Class (SOCs) and Preferred Terms (PTs) for all safety population subjects. SAEs must be collected from the date of informed consent and will be assessed up to 30 days after the end of infusion of the last period.

7.6.3 *Adverse Events*

All AEs will be coded and grouped into PT by SOC, using current version of Medical Dictionary for Regulatory Activities (MedDRA). All recorded AEs will be summarized and listed by SOCs, PTs and treatment group.

Non-serious AEs with onset time from the start of study drug infusion, until 24 hours after end of infusion in each treatment period of dosing in each period will be included in the summary tables. Events will be assigned to the study treatment administered to the subject. The proportion of subjects having an adverse event will be calculated as the number of subjects experiencing the event, divided by the total number of subjects receiving study treatment.

All AE listings will indicate the unique subject identifier, age, gender, current treatment, the date and time of onset, the date and time of resolution, day of onset relative to the start of treatment, action taken, investigator's assessment of severity and relationship to study drug. Additional listings will be provided for adverse events leading to discontinuation and adverse events without recorded resolution. Summaries of adverse events will include adverse events, adverse events by intensity and adverse events by relationship.

Where a subject has the same adverse event, based on preferred terminology, reported multiple times in a single analysis period, the subject will only be counted once at the preferred terminology level in adverse event frequency tables.

Where a subject has multiple adverse events within the same system organ class in a single analysis period, the subject will only be counted once at the system organ class level in adverse event frequency tables.

When a subject has the same adverse event, based on preferred terminology, reported multiple times in a single analysis period, the following criteria, in order of precedence, will be used to select the event to be included in summary tables:

- Relationship to study medication
- Intensity of event
- Onset date and time

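### The by-treatment SAE summary has no attribution rule and no common window per period, so SAE follow-up becomes unequal if dropout or delay differs by treatment (minor)

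*SAP*

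**What the plan says.** SAP 8.1 includes SAEs in the summary tables if onset is "on or after the start date of study drug infusion until 30 days after the end of infusion of the last period". It sets no cut-off within a period. The bullet above it gives non-serious AEs the same short window in every period: "until 24 hours after end of infusion in each treatment period of dosing".

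SAP 7.6.3 makes the tables comparative: "All recorded AEs will be summarized and listed by SOCs, PTs and treatment group". On attribution it says only: "Events will be assigned to the study treatment administered to the subject". The percentage is subjects with the event over subjects treated, with no allowance for time at risk. SAP 7.6.2 describes the SAE-specific output only as a listing, so SAEs reach by-treatment tables through 7.6.3 and 8.1.

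On timing, Protocol Table 2-2 states: "Washout between periods should be at least 5 days and no more than 4 weeks". SAP 6.1 says that the treatment days of Periods 1 and 2 "are followed by a washout period of at least 7 days but no more than 4 weeks". Protocol Table 2-2 says that SAEs "will be assessed up to 30 days after the end of infusion of the last period", and Protocol 9.2.1 requires collection of those occurring "within 30 days of discontinuation of dosing".

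**The concern.** In a crossover, an SAE that starts after Period 1 or 2 can be credited to that period's treatment only until the next infusion. After the last infusion the clock runs for 30 days. A subject who leaves after Period 1 or 2 turns that treatment into the last one, and Protocol 9.2.1 then gives it 30 days. A next visit postponed after a poorly tolerated infusion also lengthens that infusion's window. Postponement is plausible under the protocol's own rules: Protocol 5.1 applies blood pressure and heart rate limits on each treatment day and asks for laboratory abnormalities to be corrected before the next period.

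What is at stake is the reading of the SAE percentages for BMS-986231, NTG and placebo. Background heart failure events weeks after a 5-hour infusion would count more often against a treatment that was followed for longer. Because the SAP does not say which treatment owns an SAE that starts in washout, two programmers could also produce different tables. With 42 subjects, moving one subject's SAE shifts a treatment's percentage by about 1/42 = 2.4 points.

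**Working it through.** The documents give no figure for SAE follow-up, so there is none to reproduce. The check is how many days each treatment is exposed to SAE counting.

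**Inputs.** Six sequences allocated equally (SAP 2.2), so each treatment falls in Periods 1, 2 and 3 for one third of subjects each; 42 subjects, 7 per sequence. Washout w is 5 to 28 days (Protocol Table 2-2) or 7 to 28 (SAP 6.1). The last period has 30 days (SAP 8.1, Protocol 9.2.1). The 15% dropout allowance is from SAP 5.

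**Assumptions.** SAEs go to the most recent treatment; one common w; *last period* means each subject's own last period; leavers are followed for the full 30 days.

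**Step 1: nobody leaves, equal washouts.** Mean window for every treatment = (30 + 2w)/3. At w = 5 this is 40/3 = 13.3 days. The ratio between treatments is 1.00 at any w.

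**Step 2: 15% of subjects given BMS-986231 in Period 1 or 2 leave after it, and nobody leaves after another treatment.**

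- BMS-986231: [30 + 2(0.15×30 + 0.85w)]/3 = (39 + 1.7w)/3.
- Placebo follows BMS-986231 in three sequences (twice in Period 3, once in Period 2), reached by 85%. It precedes BMS-986231 in the other three, reached by all. Mean = (2×0.85×30 + 0.85w + 3w)/(3×0.85 + 3) = (51 + 3.85w)/5.55. NTG is the same by symmetry.

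| w (days) | No dropout, all treatments | BMS-986231 | Placebo | Ratio |
|---|---|---|---|---|
| 5 | 13.3 | 47.5/3 = 15.8 | 70.25/5.55 = 12.7 | 1.25 |
| 7 | 14.7 | 50.9/3 = 17.0 | 77.95/5.55 = 14.0 | 1.21 |
| 14 | 19.3 | 62.8/3 = 20.9 | 104.9/5.55 = 18.9 | 1.11 |
| 28 | 28.7 | 86.6/3 = 28.9 | 158.8/5.55 = 28.6 | 1.01 |

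**Step 3: other assumptions.**

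- *Harsher dropout.* Six leavers, about 15% of all 42, every one after BMS-986231 (3 in Period 1, 3 in Period 2). At w = 5, BMS-986231 has (560 + 6×25)/42 = 16.9 days. Placebo loses 4.5 exposures (3.0 in Period 3, 1.5 in Period 2), giving (560 − 3×30 − 1.5×5)/37.5 = 12.3. The ratio is 1.37. At w = 7, 14 and 28 it is 1.31, 1.16 and 1.01.
- *Milder dropout.* With two such leavers, the ratio is 1.12 at w = 5 and 1.00 at w = 28.
- *Delay only.* If every washout after BMS-986231 were 14 days and every other one 7, the windows would be 58/3 = 19.3 and 44/3 = 14.7 days, ratio 1.32.

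**Step 4: in events.** In Step 2, 28 subjects get BMS-986231 in Period 1 or 2, and 0.15 × 28 = 4.2 leave. At w = 5 each adds 25 days: 4.2 × 25 = 105 subject-days, or 0.29 subject-years. The documents give no SAE rate. Assuming 0.5 to 2 per subject-year, this is about 0.14 to 0.6 extra SAEs on BMS-986231.

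**The case against.** A reader might infer that the rule gives a poorly tolerated treatment more SAE follow-up by construction. The documents do not support that. Equal allocation to six sequences gives every treatment the same mean window unless dropout or delay differs by treatment. The gap between 5 and 30 days within one subject is an effect of period position, which the balanced sequences average out. A stopped infusion does not end participation (Protocol 7.4), so poor tolerance need not become dropout. A subject who withdraws consent for further contact (Protocol 8.2) may contribute less than 30 days.

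The attribution rule used here is also an inference. The SAP 8.1 bullets follow a lead-in about missing or incomplete onset times, and SAP 8.1 defers other handling to sponsor safety conventions that are not among the documents and might settle the matter. Even so, the SAP gives no other window for SAE tables.

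The scenarios are one-sided: all leavers follow BMS-986231, and the largest ratios need the shortest washout for everyone. Safety output is descriptive, with no planned test. SAP 7.6.3 already requires AE listings to show current treatment and day of onset relative to start of treatment, so late SAEs can be identified there.

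All of this limits the size of the point. It does not remove the missing attribution rule, or the contrast with non-serious AEs, which have one window in every period. It is also a fair objection that a short window alone would drop later SAEs from the comparison, so it should supplement the full-window table.

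**Conclusion.** The point holds conditionally and is minor. As written, the SAP allows SAE time at risk to depend on period position, and balance across treatments then depends on dropout and washout length being unrelated to treatment. If 15% leave after BMS-986231 in Period 1 or 2 and nobody leaves after another treatment, its mean window is about 1.25 times that of placebo at a 5-day washout, 1.11 at 14 days and about 1.0 at 28 days. With no differential dropout or delay the ratio is 1.00. These figures assume attribution to the most recent treatment, a common washout and complete 30-day follow-up of leavers. Under the assumed SAE rates the dropout scenario at a 5-day washout adds less than one event. No efficacy endpoint is affected.

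**What to change.** In SAP 8.1 and 7.6.3:

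- State that an SAE is attributed to the most recent treatment received.
- Add a by-treatment SAE summary with one window in every period, no longer than the shortest permitted washout: onset from start of infusion to 5 days after its end, or to the next infusion if earlier. Five days fits within the minimum in both documents.
- Keep the full-window SAE table and the listing.

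Separately, reconcile the minimum washout, which is 5 days in the current protocol and 7 days in SAP 2.1 and 6.1. SAP 2.4 says that it is based on protocol version 02, whereas the current protocol is version 05.

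The cost is SAP wording, one table filter and one extra table. SAEs starting more than 5 days after an infusion would appear only in the full-window table and the listing.

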8.2 Baseline Measurements

For analyses involving baseline, the baseline value is defined by the last value prior to the start of infusion, unless otherwise noted.

When there is a missing baseline assessment it will not be imputed.

8.3 Multiple Measurements

For longitudinal summaries of data, if there are multiple records within the same Hour ranges, then the value closest to the time of the planned time points is selected unless specified otherwise.

Laboratory Measurements

For tabulations of changes from baseline or shift analyses, if multiple laboratory measurements are obtained within the same nominal visit, then the measurement obtained on the day closest to the target day for that nominal visit will be used; in the case of a tie, the measurement obtained on the earlier day will be used in the analyses.

For tabulations of incidence of marked abnormalities (e.g. ALT > 3xULN), if multiple laboratory measurements are obtained within the same nominal visit, then the worst measurement within the nominal visit window nominal visit will be used.

Vital Signs and ECGs

If multiple vital sign or ECG measurements are obtained within the same nominal visit, then the measurement obtained on the day closest to the target day for that nominal visit will be used; in the case of a tie, the measurement obtained on the earlier day will be used in the analyses.

8.4 Pharmacokinetic Summaries

In-text Tables

For in-text pharmacokinetic tables, coefficient of variation (%CV) will be reported as integers. For other statistics except for standard deviations, values of 100 or higher will be presented as integers, values of 10 - <100 will be displayed to one decimal place, and values of 1 - < 10 will be displayed to two decimal places. Values less than 1 will be displayed to three decimal places. Ratios will also be displayed to three decimal places. Standard deviations will be reported to a precision of 1 decimal place more than the mean.

Handling of Non-Quantifiable Concentrations

For the summaries of plasma concentration-time data, concentrations that are less than the lower limit of quantification (LLOQ) should be displayed as “< LLOQ” in the listings and be treated as missing in summary tables and plots.

All available plasma concentration-time data will be included in the PK data set and listed accordingly.

Treatment of Outliers

Individual plasma concentrations, if deemed to be anomalous, may be excluded from the analysis following a review of available documentation (e.g., bioanalytical report, clinical data). Any such exclusion will be clearly listed in the study report along with justification for exclusion.

Entire plasma concentration-time profiles for a subject may be excluded following review of available documentation (e.g., bioanalytical report, clinical data). However, results of analysis with and without the excluded profiles may be presented in the study report. Any such exclusion will be clearly listed in the study report along with justification for exclusion.

PK Exclusions⁵

PK Analysis, Reporting, and Exclusion criteria should follow the BMS PK Harmonization document Version 3.0.

9 CONTENT OF REPORTS

Statistical components for the clinical study report will be based on the content of this statistical analysis plan (SAP). Details of the tables, listings, and figures to be prepared for interim analyses and the final CSR will be included in a study-specific Data Presentation Plan (DPP).

10.1002/anie.201907002

• [Home](#) | [About](#) | [Services](#) | [Contact](#) | [Blog](#)

For more information, contact the Office of the Vice President for Research and the Office of the Vice President for Student Affairs.

For more information, contact the Office of the Vice President for Research and the Office of the Vice President for Student Affairs.

Page 1 of 1

For more information, contact the Office of the Vice President for Research and Economic Development at [contact] or [contact].

www.english-test.net
